5.2.1. Additional Exclusion Criteria for Part B (Patients with Atopic Dermatitis)

- 39. Are currently experiencing or have a history of other concomitant skin conditions (for example, psoriasis or cutaneous lupus) that would interfere with the evaluation of the effect of the study medication on AD.
- 40. participants who, in the opinion of the investigator, are currently experiencing or have a history of erythrodermic, refractory, or unstable skin disease that requires frequent hospitalizations and/or IV treatment for skin infections that may interfere with their participation in the study.
- 41. Have a history of eczema herpeticum
 - a. within 6 months prior to screening, or
 - b. 2 or more episodes during lifetime.
- 42. participants who are currently experiencing a skin infection that requires treatment or is currently being treated with topical or systemic antibiotics.

- Note: Participants may not be rescreened until at least 4 weeks after the date of their previous screen failure and at least 2 weeks after the resolution of the infection.
- 43. Have a history of TCS use suggestive of a high risk for TCS withdrawal, for example, a history of prolonged or frequent use of moderate- to high-potency TCS, especially on the face (Hajar et al. 2015), such that, in the opinion of the investigator, the participant will be unable to withdraw and abstain from TCS for several weeks during the study.
- 44. have any serious concomitant illness that is anticipated to require the use of systemic corticosteroids or otherwise interfere with study participation or require active, frequent monitoring (for example, unstable chronic asthma requiring hospitalization and/or systemic corticosteroids in the 6 months prior to screening).
- 45. have been treated with the following therapies:
 - a. Other mAb (for example, ustekinumab, omalizumab, dupilumab, tralokinumab, and lebrikizumab (whether approved or investigational) within 5 half-lives prior to randomization (Visit 2).
 - b. Received any parenteral corticosteroid administered by intramuscular or IV injection within 2 weeks prior to study entry (Visit 1) or within 6 weeks prior to planned randomization (Visit 2) or are anticipated to require parenteral injection of corticosteroids during the study.
 - c. Have had an intra-articular corticosteroid injection within 2 weeks prior to study entry (Visit 1) or within 6 weeks prior to planned randomization (Visit 2).
 - d. Have used any of the following topical medications within 1 week prior to randomization (Visit 2):
 - topical corticosteroids or topical immune modulators (for example, tacrolimus or pimecrolimus)

Note: pimecrolimus may not be available in all regions, including Japan.

- topical phosphodiesterase type 4 inhibitor, or
- topical Janus kinase inhibitor.

Note: Intranasal or inhaled steroid use is allowed during the trial.

- 46. have received the following excluded medications/treatments within 4 weeks prior to randomization (Visit 2) or plan to use during the study:
 - a. oral systemic corticosteroids and leukotriene inhibitors.
 - b. systemic immunomodulators, including, but not limited to, cyclosporine, methotrexate, mycophenolate mofetil, azathioprine, and Janus kinase inhibitors (such as tofacitinib, ruxolitinib, baricitinib, upadacitinib or abrocitinib).
 - c. sedating antihistamines including, but not limited to, alimemazine, chlorphenamine, clemastine, cyproheptadine, diphenhydramine, hydroxyzine, ketotifen, and promethazine.

Note: Participants may use newer, less sedating antihistamines (for example, fexofenadine, loratadine, and cetirizine).

d. any other systemic therapy used to treat AD or symptoms of AD (approved or off-label use).

- e. phototherapy, including therapeutic phototherapy (psoralen plus ultraviolet-A and ultraviolet-B), excimer laser, or tanning beds.
- 47. patients with a positive beta-D-glucan test at screening and a confirmed diagnosis of pneumocystis pneumonia will be excluded.
- 48. have experienced hypersensitivity to the active substance or to any of the excipients.
- 49. For Japanese participants only: have evidence of, or a positive test for, HBV infection, defined as:
 - a. positive for hepatitis B surface antigen (HBsAg), or
 - b. positive for hepatitis B core antibody (HBcAb) and positive HBV DNA, or
 - c. positive for hepatitis B surface antibody (HBsAb) and positive for HBV DNA.

Note: Patients who are positive for HBcAb or HBsAb and negative for HBV DNA may be enrolled in Part B of the study. In this case, repeat testing for HBV DNA is required at least once every month during the study.

5.3. Lifestyle Considerations

Throughout the study, participants must adhere to lifestyle restrictions as outlined by the CRU and in the study procedures. Participants may undergo medical assessments and a review of compliance with requirements before continuing in the study.

5.3.1. Meals and Dietary Restrictions

During the confinement period (where applicable), participants will consume only food and beverages that are provided to them by the CRU staff. Standard meals (for example, breakfast, lunch, dinner, and snack) will be provided to the participants while resident at the CRU.

In Part A (SAD) and Part B (MAD), participants will be required to fast for approximately 4 hours before study intervention administration. Water is permitted. Participants may eat approximately 2 hours postdose. A normal diet may be consumed at all other times during the study.

In Part C (PO QD prednisone), the participants will be fasted overnight (at least 10 hours) prior to dosing and refrain from consuming water from 1-hour predose until 2-hour postdose, excluding the amount of water consumed at dosing. Food is allowed 4 hours postdose. At all other times during the study, participants may consume water ad libitum.

For all outpatient visits in Parts A, B, and C, participants will be required to fast approximately 10 hours before visits that include clinical chemistry testing. Water is permitted.

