4.2. Scientific Rationale for Study Design

Study KMAA is the first-in-human dose study that will characterize the safety, tolerability, and PK of single doses of LY3872386 in healthy participants, multiple doses of LY3872386 in patients with AD, and multiple dose levels of prednisone in healthy participants. Participants receiving prednisone PO QD will not be blinded with a placebo. Blinding of subjects to prednisone was not deemed necessary as only objective safety and PD biomarker results following prednisone or LY3872386 administration will be compared. A lack of blinding would not be expected to affect these results. The data generated in this study will guide the design of the subsequent clinical trials.

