7.1.6.2. Glucose and HbA1c Values for Permanent Discontinuation

Any of these laboratory results with no other obvious cause in the opinion of the investigator:

- If 2 fasting glucose measures are ≥126 mg/dL
- If 1 fasting glucose measure is \geq 126 mg/dL and glycated hemoglobin level is \geq 6.5% (48 mmol/mol) (ElSayed et al. 2023)

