10.2. Appendix 2: Clinical Laboratory Tests

The tests detailed in the table below will be performed by the central laboratory except for the following which will be performed at the local laboratory:

- Safety testing for immediate participant assessment
- Screening assessments in Part A and Part C.

In circumstances where the sponsor approves local laboratory testing in lieu of central laboratory testing (in the table below), the local laboratory must be qualified in accordance with applicable local regulations.

Protocol-specific requirements for inclusion or exclusion of participants are detailed in Section 5 of the protocol.

Additional tests may be performed at any time during the study as determined necessary by the investigator to address any immediate patient safety concerns.

Investigators must document their review of the laboratory safety results.

Laboratory results that could unblind the study will not be reported to investigative sites or other blinded personnel.

Safety Laboratory Tests

TH	GILL LGI
Hematologya	Clinical Chemistrya
Hematocrit	Sodium
Hemoglobin	Potassium
Erythrocyte count (RBC)	Bicarbonate
Mean cell volume	Chloride
Mean cell hemoglobin	Calcium (total)
Mean cell hemoglobin concentration	Phosphorus/Phosphate
Leukocytes (white blood cells [WBCs])	Glucose (fasting)
Platelets	Blood urea nitrogen (BUN)
Differential WBC (absolute counts) of	Creatinine
Neutrophils	Total protein
Lymphocytes	Albumin
Monocytes	Total bilirubin
Eosinophils	Alkaline phosphatase (ALP)
Basophils	Aspartate aminotransferase (AST)
B Cells	Alanine aminotransferase (ALT)
T Cells	Gamma-glutamyl transferase (GGT)
NK cells	Insuline
Hemoglobin A1c	Bedside Glucose Monitoring (fasting)f
Urinalysis ^a	Serum Immunoglobulinsa
Specific gravity	IgA
рН	IgM
Protein	IgE
Glucose	IgG
Ketones	IgD
Bilirubin	192
Urobilinogen	Fasting Lipid Panel ^a
Leukocytes	Total cholesterol
Blood	Triglycerides
Nitrite	Low-density lipoprotein (LDL)
	High-density lipoprotein (HDL)
Microscopic examination of sedimentb	
	LDL/HDL ratio
H. D. C.	T W D C W all
Urine Drug Screen ^c	Hepatitis B surface antigeng,h
Amphetamine	Hepatitis B core antibodyg,h
Barbiturates	Hepatitis B surface antibodyg,h
Benzodiazepines	Hepatitis B DNAh
Cocaine	Hepatitis C antibodyg,h
Cannabis	riepatitis C antibody
Methylenedioxymethamphetamine (MDMA)	
Opiates	
Oxycodone	
Phencyclidine	
Tricyclic antidepressants	
Cotinine (nicotine)	
	gh
Ethanol breath testing ^c	$HIV^{g,h}$
QuantiFERON®-TB Gold test or TST	Pregnancy test ⁱ

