Beta D-glucand	FSH ⁱ
Cortisol (serum, cosyntropin stim, and urine)	Thyroid-stimulating hormone (including T3/T4 tests) Syphilis test (including RPR and TPPA as
	appropriate) ^g

Abbreviations: DNA = deoxyribonucleic acid; ED = early discontinuation; FSH = follicle-stimulating hormone; HIV = human immunodeficiency virus; Ig = immunoglobulin; NK cell = natural killer cell; RBC = red blood cell; RPR = Rapid Plasma Regain; TPPA = Treponema Pallidium Particle Agglutination.

Note: Results of these assays will be validated by the local laboratory at the time of testing. Additional tests may be performed or auto calculated by the laboratory as part of its standard panel that cannot be removed. Some of the above parameters are calculated from measured values. The omission of calculated values will not be considered as a protocol violation.

- a To be done centrally. If needed for safety, site may also perform locally.
- b Test only if dipstick result is abnormal.
- ^c Urine drug screen and ethanol breath testing may be repeated prior to admission to the clinical research unit and at other times indicated in the Schedule of Activities. Unscheduled testing is allowed.
- d Evaluation of beta-D-glucan may be performed at a local laboratory. Beta-D-glucan is required at screening for Part B only (to be performed centrally), and if an investigator believes it is warranted, at subsequent visits (may be performed centrally or locally), a beta-D-glucan test may be included in the work up panel at any time during the study. If the beta-D-glucan test is positive, pneumocystis pneumonia (PCP) needs to be ruled out. If PCP is ruled out and the investigator deems the patient fit to continue, the patient may continue in the study. If a patient has a confirmed diagnosis of PCP during the study, the patient must discontinue the study.
- e Not performed at screening.
- f Bedside glucose monitoring is performed using standard glucose monitors and capillary blood taken from fingerstick. Fasting should be approximately 2 hours, at a minimum.
- g Performed at screening only.
- h These tests may be waived if performed within 6 months prior to screening, and if test results are available for "review" for hepatitis B, C, and HIV.
- i To be performed on all female participants.

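### Part A within-arm change in fasting lipids, and in outpatient glucose and insulin, mixes drug effect with a move from a 4-hour to a 10-hour fast, as does the raw lipid comparison with 30-day prednisone

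*Protocol*

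**What the plan says.** Protocol Section 5.3.1 gives different fasts for different occasions. For Parts A and B, "participants will be required to fast for approximately 4 hours before study intervention administration", and "A normal diet may be consumed at all other times during the study". For Part C, "the participants will be fasted overnight (at least 10 hours) prior to dosing". For outpatient visits in all three parts, "participants will be required to fast approximately 10 hours before visits that include clinical chemistry testing".

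Appendix 2 (Section 10.2) lists chemistry glucose and the lipid panel as fasting tests but gives no duration. For bedside glucose, also labelled fasting, footnote f says "Fasting should be approximately 2 hours, at a minimum". Section 7.1.6.2 has a criterion that begins "If 2 fasting glucose measures are" and sets the level at 126 mg/dL or above. It does not say which of these fasts makes a value count.

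SAP Section 10.6.3 summarises chemistry by part, treatment and time point, with change from Day 1 predose. Protocol Section 4.2 justifies open-label prednisone on the ground that "only objective safety and PD biomarker results following prednisone or LY3872386 administration will be compared".

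**The concern.** Protocol Section 2.3 names raised triglycerides and raised glucose among the potential risks consistent with glucocorticoid pharmacology. Both, like insulin, are measured under a fasting label because the value can depend on the time since the last meal. If the baseline and follow-up samples are taken under different fasts, the change within an arm contains a fasting component as well as a drug component. If the longer fast lowers the value, a real rise could be reduced or hidden in the change-from-baseline tables.

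The same applies to a raw comparison with Part C, which has no placebo arm and whose dosing-day samples follow an overnight fast.

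**Working it through.** The plan gives no figure to reproduce. The check sets the sampling rules side by side and then works through an additive model.

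**Sampling conditions** (schedules in Section 1.3, fasts from Section 5.3.1 and Appendix 2)

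| Sample | Setting | Fast in the visible text |
|---|---|---|
| Part A Day 1 predose: lipids, glucose, insulin | Inpatient | About 4 h, before dosing |
| Part A inpatient chemistry after Day 1 | Inpatient | None stated |
| Part A V804: the only scheduled follow-up lipids | Outpatient | About 10 h |
| Part A V801 to V808: glucose, insulin | Outpatient | About 10 h |
| Part A bedside glucose: Day -1, Day 1 predose and 12 h, 24 h, 36 h, Day 7 | Inpatient | About 2 h minimum (Day 1 predose also under the 4 h rule) |
| Part C 30-day groups, lipids: Day 1 and Day 30 predose | Inpatient | At least 10 h |
| Part C 7-day group, lipids | – | No panel scheduled |
| Part C chemistry before first dose | – | Screening and one later draw before Day 1; no Day 1 draw; no inpatient fast stated |

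The Part A lipid row was read by column. There are 18 columns: screening, Day -1, Days 1 to 7, V801 to V808, and early discontinuation (1 + 1 + 7 + 8 + 1 = 18). The marks fall in column 3 (Day 1 predose), column 13 (V804) and column 18 (early discontinuation). Column 13 also carries the HbA1c sample that the amendment summary dates to Day 29.

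**Model.** Let d be the mean drug effect in Part A, d_C the mean prednisone effect, and s the mean change caused only by moving from a 4 h to a 10 h fast.

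- Part A LY3872386, raw change: d + s
- Part A placebo, raw change: s
- LY3872386 minus placebo: (d + s) - s = d
- Part C lipids, 30-day groups, raw change: d_C, since both samples follow at least 10 h
- Raw Part A minus Part C: (d + s) - d_C = (d - d_C) + s
- Placebo-adjusted Part A minus Part C: d - d_C

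The documents give neither the size nor the sign of s. Assume s from -20 to +10 units and, for illustration, d = d_C = 8:

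| s | Raw LY3872386 change | LY3872386 minus placebo | Raw Part A minus Part C | Placebo-adjusted Part A minus Part C |
|---|---|---|---|---|
| -20 | -12 | 8 | -20 | 0 |
| -10 | -2 | 8 | -10 | 0 |
| -5 | 3 | 8 | -5 | 0 |
| 0 | 8 | 8 | 0 | 0 |
| +5 | 13 | 8 | 5 | 0 |
| +10 | 18 | 8 | 10 | 0 |

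The raw change and the raw cross-part lipid difference are each wrong by exactly s. At s = -10, a true rise of 8 appears as a fall of 2. The placebo contrast is unaffected.

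**The case against.** The strongest reply is that Part A is randomised. Placebo is given at the same time and by the same route within each cohort, under the same fasting rules, and is pooled within the part. A reader might infer that the whole glucocorticoid metabolic signal is confounded. It is not: an additive shift cancels in LY3872386 minus placebo. What remains is that the SAP plans no placebo-corrected laboratory summary; placebo correction appears only in its ECG analysis. Individual values assessed by the blinded investigator for dose decisions (Section 6.6.1) have no such cancellation.

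A reader might also infer that Part A glucose and insulin baselines differ from Part C in the same way as lipids. The documents do not support that. Neither Part C schedule shows a Day 1 chemistry draw, and no inpatient fast is stated for the draw that precedes it. Outpatient levels in both parts carry the same 10 h rule, so levels can be compared there. Section 4.2 does not name glucose or lipids, and the SAP specifies no cross-part metabolic contrast.

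A third tempting inference is that bedside readings taken after a meal will trigger discontinuation. Bedside monitoring is scheduled only in Part A, which gives one dose, so little dosing is left to discontinue. Section 7.1.6.2 also excludes results with another obvious cause in the investigator's opinion. The undefined term remains a matter of wording.

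Three limits on the point stand. The schedule comment columns are redacted and may hold fasting instructions. The 4 h rule is a dosing fast, and actual Day 1 fasts may be longer. HbA1c is sampled in Part A with no fasting rule and gives a separate glycaemic reading, though not a lipid one.

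**Conclusion.** The point holds for Part A within-arm change in fasting lipids, and in chemistry glucose and insulin at outpatient visits. It also holds for raw Part A lipid change set against the 30-day prednisone groups. In each case the error equals s. It does not hold for LY3872386 against placebo under an additive shift, is not shown for glucose or insulin against Part C, and does not arise for lipids in the 7-day group.

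The conclusion rests on the fasts in the visible text being those actually applied, and on a shift common to both Part A arms. The numerical range is assumed. Confidence is moderate, and the change is worth making because samples drawn under mixed, unrecorded fasts cannot be corrected afterwards.

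**What to change.** - Reconcile Section 5.3.1, Appendix 2 footnote f and the term fasting glucose in Section 7.1.6.2, so that all samples labelled fasting share one stated sampling condition. One option is to apply the outpatient condition of about 10 h, already in Section 5.3.1, to Part A Day 1 predose and inpatient chemistry and lipids. If the redacted comments already say this, Section 5.3.1 should say it too. How the discontinuation criterion itself should read is for the sponsor to settle.
- Record hours since the last meal with each glucose, insulin and lipid sample.
- Report bedside glucose taken after a shorter fast separately.
- In SAP Section 10.6.3, add placebo-adjusted change for these analytes in Part A, and use it for any comparison with Part C. This removes the fasting shift only; Part C still has no placebo of its own.

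The cost is protocol and SAP wording, one extra data field, and a longer fast or later breakfast on inpatient sampling days, including before dosing on Day 1. No extra samples are needed.

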5.3.2. Substance Use: Caffeine, Alcohol, and Tobacco

For Parts A, B, and C, consumption of caffeine-containing beverages is permitted during the outpatient portions of the study. For Parts A and C, participants will abstain from ingesting caffeine- or xanthine-containing products (for example, coffee, tea, cola drinks, and chocolate) from check-in and through discharge from the CRU.

For Parts A and C, participants will not consume alcohol from check-in and through discharge from the CRU. For Part B, participants should not consume alcohol for at least 24 hours prior to dosing and at least 2 days postdose. During outpatient periods, all participants should be advised to limit alcohol consumption to no more than 2 units per day.

Participants should be willing and be able to abide by smoking restrictions at the CRU during both the inpatient period and outpatient visits.

Study participants should be instructed not to donate blood, blood products, and/or tissue during the study or for 14 weeks following the final visit of the study.

5.3.3. Activity

Participants will abstain from strenuous exercise for approximately 5 days before each blood collection for clinical laboratory tests. Participants may participate in light recreational activities during studies (for example, watching television and reading).

5.4. Screen Failures

A screen failure occurs when a participant consents to participate in the clinical study but is not subsequently assigned to the study intervention or enrolled in the study. A participant who is an alternate in a study group/cohort may be enrolled in the next group/cohort if within the screening window or may screen for a subsequent group, unless the participant was a screen fail.

As Part A and Part C are healthy participant-only studies, individuals who do not meet the criteria for participation in this study (screen failure) may not be rescreened, although screening tests such as clinical laboratory tests and vital signs or ECGs may be repeated at the discretion of the investigator. If subjects have minor deviations in screening assessments (for example, vital signs), these may be repeated at the investigator's discretion to confirm eligibility.

As Part B participants are patients with AD, individuals who do not meet the eligibility criteria for participation in this study (screen failure) may not be rescreened until at least 4 weeks after the date of their previous screen failure and at least 2 weeks after resolution of a skin infection, unless the rescreening is for administrative reasons (see below). Blood tests may be repeated at the discretion of the investigator during screening without being considered a screen failure. Participants may be rescreened once. When rescreening is performed, the individual must sign a new ICF and will be assigned a new identification number.

Allowed Rescreening for Administrative Reasons

An individual may be rescreened once for an administrative reason, such as falling out of the screening window because of scheduling conflicts. The sponsor does not need to approve rescreening for administrative reasons. The rescreening can start immediately after the administrative reason has been resolved.

5.5. Criteria for Temporarily Delaying Enrollment/Randomization/ Administration of Study Intervention of a Participant

Not applicable.

6. Study Interventions and Concomitant Therapy

Study intervention is defined as any investigational intervention(s), marketed product(s), placebo, or medical device(s) intended to be administered to or used by a study participant according to the study protocol.

6.1. Study Interventions Administered

This table lists the interventions used in this clinical study.

Intervention Name	LY3872386	Placebo (0.9% sodium chloride solution)	Prednisone
Dosage Level(s)	mg/vial (single administration, CCI for 12 weeks, and CCI for 12 weeks)	N/A	mg (CCI x 30 days), and mg (CCI x 30 days), and mg (CCI x 7 days)
Route of Administration	IV and SC Approximately CCI min IV infusion	Same as LY3872386 administration	Oral
Authorized as defined by EU Clinical Trial Regulation	Not authorized in EU	Authorized, not used according to authorization	Authorized, not used according to authorization

Abbreviations: EU = European Union; IV = intravenous; SC = subcutaneous; CC

Packaging and Labeling

LY3872386 will be supplied by the sponsor in accordance with the current Good Manufacturing Practice. The study interventions will be labeled as appropriate for country requirements.

